#### Proportion of patients with severe neutropenia or thrombocytopenia

Proportion of patients with newly occurring CTCAE grade 4 neutropenia or thrombocytopenia will be displayed by treatment group. Results will also be provided for annual time intervals.

#### Proportion of patients with major gastrointestinal bleeding

An evaluation of the proportion of patients with major gastrointestinal bleeding will be performed. Major gastrointestinal bleeding is defined as an AE that may include one of the following MedDRA preferred terms:

Gastric haemorrhage

Gastrointestinal haemorrhage

Small intestinal haemorrhage

Oesophageal haemorrhage

Large intestinal haemorrhage

Rectal haemorrhage

Melaena

Duodenal ulcer haemorrhage

Gastric ulcer haemorrhage

Peptic ulcer haemorrhage

Large intestinal ulcer haemorrhage

Oesophageal ulcer haemorrhage

Haematochezia

Frequency tables will be prepared by treatment group. Results will also be provided for annual time intervals.

In addition, a statistical analysis of the multivariate (recurrent) major gastrointestinal bleeding data will be performed.

#### Time to study drug discontinuation due to an AE or laboratory abnormality

An evaluation of the time from randomization to study drug discontinuation due to an AE or laboratory abnormality will be performed. The variable will be based on the date and reason given on the Study Treatment Completion eCRF page. Only patients for whom the reason for stopping study medication was entered as AE or laboratory abnormality will be considered. The definition of the variable is:

• date of study drug discontinuation due to an AE or laboratory abnormality minus date of randomization plus 1.

The time-to-event analysis follows the description given in Section 10.4.2.1 to Section 10.4.2.4. The statistical test will be exploratory. Censoring is described in Section 10.4.3.

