#### 6.7.1.4 Gastrointestinal disturbances

Patients with gastrointestinal symptoms (including abdominal pain, nausea, vomiting, diarrhea) and/or patients who are unable to tolerate once a day study drug dosing, the following can be tried, in the order specified below:

- Change the timing of study drug administration from morning to evening and in addition, try using an anti-diarrheal agent for 2 days in case of diarrhea.
- If the symptoms still continue, try administering the daily dose as a split dose b.i.d.(twice daily). Once symptoms resolve, b.i.d. should be switched back to once daily.

Should the gastrointestinal issues persist, study drug may be discontinued if the investigator believes it is in the best interest of the patient. Novartis may be contacted by the investigator to discuss dosing options if the investigator so desires.

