# 6.7.5 Study drug discontinuation

Patients who discontinue study drug entirely before completing the study should be scheduled for the End of Treatment visit as soon as possible, at which time all of the assessments listed for Study End of Treatment visit will be performed. This will document the date and reason for stopping randomized study treatment. It must be completed for all patients. Any safety finding that leads to discontinuation of study drug should be captured on the AE eCRF.

All patients who discontinue study drug, including those who refuse to return for a final visit, will be contacted by the investigational site for safety evaluations during the 28 days following the last dose of study drug. All patients must have the 28 Day Follow-Up completed after they discontinue from the study drug.

All iron chelation therapies given to a patient after the last dose of study treatment must be recorded in the 'Chelation therapies given since discontinuation of study drug' eCRF during the 28 day follow up, Evaluation and Survival phases of the study. Patients who discontinue study drug and do not wish to be followed for post-treatment evaluations and survival should be considered withdrawn from the study after the final visit assessments are performed or when it is clear that the patient will not return for these assessments. The End of Treatment eCRF should be completed and the Study Evaluation Completion visit should be performed at this time.

All patients must be followed for AEs and SAEs for 28 days after the last dose of study treatment. Patients lost to follow up should be recorded as such on the Study Evaluation Completion eCRF. If the patient is at the end of treatment, the End of Treatment eCRF must also be completed. For patients who are lost to follow-up, the investigator should show "due diligence" by documenting in the source documents steps taken to contact the patient, e.g., dates of telephone calls, registered letters, etc.

The investigator must contact IVRS/IWRS to register discontinued patients.

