#### 6.7.6.1 End of Treatment

If study drug is discontinued, IVRS is to be notified and the End of Treatment Page is to be completed with the 'last known date the patient took study drug' and one of the following reasons:

- Adverse Event
- Abnormal laboratory value(s)
- Abnormal test procedure result(s)
- Protocol deviation
- Subject withdrew consent
- Lost to follow-up
- Administrative problems
- Death
- Disease progression
- Pregnancy
- Physician's decision
- Treatment duration completed as per protocol
- Subject / Guardian Decision

• Study terminated by sponsor

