## 7.5.1 Adverse events

An adverse event for the purposes of this protocol is the appearance of (or worsening of any pre-existing) undesirable sign(s), symptom(s), or medical condition(s) occurring after signing the informed consent even if the event is not considered to be related to the study drug(s). However, it must be noted that MDS is not considered an adverse event. MDS is a required condition for study entry and is expected to be reported as Medical History for all patients. Time to disease progression is a secondary efficacy endpoint. Please refer to Section 6.1 for the protocol-specific definitions of study drug and study treatment.

Adverse events (but not serious adverse events) occurring before starting study treatment but after signing the informed consent form are recorded on the Medical History/Current Medical Conditions eCRF. Abnormal laboratory values or test results that induce clinical signs or symptoms, are considered clinically significant, require therapy (e.g., any hematological abnormality that requires transfusion or cytokine treatment), or interruption of study medication should be recorded on the Adverse Events eCRF under the signs, symptoms or diagnosis associated with them. Abnormal Laboratory values that do not meet this criteria are not reported as Adverse Events. SAEs occurring after signing the Informed Consent are recorded on the Adverse Event eCRF.

The occurrence of adverse events should be sought by non-directive questioning of the patient at each visit during the study. Adverse events also may be detected when they are volunteered by the patient during or between visits or through physical examination, laboratory test, or other assessments. As far as possible, each adverse event should be evaluated to determine:

- 1. The severity grade (mild, moderate, severe)
- 2. Its relationship to deferasirox (suspected/not suspected)

- 3. Its duration (start and end dates or if continuing at final examination)
- 4. Action taken (no action taken; study drug dosage adjusted/temporarily interrupted; study drug permanently discontinued due to this adverse event; concomitant medication taken; non-drug therapy given; hospitalization/prolonged hospitalization)
- 5. Whether it is serious, where a serious adverse event (SAE) is defined as one which:
  - Is fatal or life-threatening
  - Results in persistent or significant disability/incapacity
  - Constitutes a congenital anomaly/birth defect

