2.8 Safety analyses

As stated in the protocol (Section 3.2), one of the secondary objectives was to evaluate safety, in particular to assess the levels of increased risk for pre-specified adverse events (renal dysfunction, neutropenia, thrombocytopenia, gastrointestinal bleeding, and laboratory abnormalities) that would be clinically unacceptable in the context of the level of benefit that is likely to be provided by iron chelation using deferasirox in MDS patients with iron overload.

Endpoints for the secondary safety objectives are as follows:

- 1. Proportion of patients with significant renal dysfunction
- 2. Proportion of patients with newly occurring moderate or severe neutropenia or thrombocytopenia
- 3. Proportion of patients with major gastrointestinal bleeding
- 4. Time to study drug discontinuation due to an adverse event or laboratory abnormality
- 5. Incidence of other adverse events and laboratory abnormalities

The first four endpoints are defined and evaluated as follows:

Proportion of patients with significant renal dysfunction defined as serum creatinine ≥ 2 times ULN at two consecutive assessments (at least 7 days apart) Frequency tables by treatment group will be prepared along with a two-sided 95% confidence interval for evaluation of DFX in contrast to placebo. Results will also be

Endpoint	Analysis
Proportion of patients with newly occurring neutropenia (absolute neutrophils count <1.0×10 ⁹ /L) or thrombocytopenia (platelets <50×10 ⁹ /L)	provided for annual time intervals.
Proportion of patients with major gastrointestinal bleeding.	
Time to study drug discontinuation due to an AE or laboratory abnormality, more specifically date of study drug discontinuation due to an AE or laboratory abnormality minus date of randomization plus 1.	The time-to-event analysis follows the description given in Section 2.5.2.2 The statistical test will be exploratory in nature. For the analysis of time from randomization to study drug discontinuation due to an AE or laboratory abnormality (see Section 2.8.3), patients who did not discontinue study medication due to an AE or laboratory abnormality will be censored at the date of study drug discontinuation.

Proportion of patients with moderate or severe anemia will be analyzed like newly occurring neutropenia.

Other analyses and other safety data (ocular and auditory examinations, electrocardiogram, and vital signs) will be also considered.

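### Time to discontinuation for an AE or laboratory abnormality is read from one completion-page reason, so a safety stop filed under another reason is censored even if the AE record names it as the cause

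*Protocol*

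**What the plan says.** Protocol 10.5.2.2 names one source for the variable: "The variable will be based on the date and reason given on the Study Treatment Completion eCRF page". It then restricts the events: "Only patients for whom the reason for stopping study medication was entered as AE or laboratory abnormality will be considered".

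Protocol 6.7.6.1 says the page is completed with the last date on drug "and one of the following reasons", followed by 14 options. Adverse Event and Abnormal laboratory value(s) are two of them. Abnormal test procedure result(s), Physician's decision and Subject / Guardian Decision are separate options.

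Protocol 10.4.3 and SAP 2.8 use the same censoring rule. In the SAP's words, "patients who did not discontinue study medication due to an AE or laboratory abnormality will be censored at the date of study drug discontinuation". SAP 2.8 names no data source and no mapping of reasons. SAP 2.1 refers back to section 10 of the protocol, and SAP section 4 declares no change to this endpoint.

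The AE page holds related information. Protocol 6.7.5 states: "Any safety finding that leads to discontinuation of study drug should be captured on the AE eCRF". Under Protocol 7.5.1 the action taken for an AE can be "study drug permanently discontinued due to this adverse event". SAP 2.8.1 plans a frequency table of AEs leading to study drug discontinuation.

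**The concern.** A stop caused by harm can reasonably be entered under a reason that does not count. Hearing loss and lens opacities are named risks (Protocol 1.3 and 6.7.1.8). They are found by audiometry and eye examination, which are test procedures and not laboratory values. For several other toxicities the protocol describes stopping as the investigator's judgement. For gastrointestinal symptoms, for example, "study drug may be discontinued if the investigator believes it is in the best interest of the patient". A site could record such a stop as a physician's decision. No section says which reason takes precedence when more than one fits.

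Two things are at stake. First, events are under-counted, and the censoring that replaces them is informative, because the patient leaves for the very cause the endpoint is meant to measure. Second, the time-to-event result and the AE table can disagree within one report, with no rule to reconcile them.

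The direction matters because the synopsis frames the safety analyses as excluding unacceptable increases in risk, using 95% intervals for risk or hazard ratios. If treatment-caused stops are missed mainly on deferasirox, the upper limit falls and the drug looks safer than it is.

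**Working it through.** **Textual check**

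1. Reasons listed in Protocol 6.7.6.1: 14. Counted as events under 10.5.2.2: 2. Censored: 14 − 2 = 12.
2. Take a patient whose AE record shows permanent discontinuation as the action, and whose completion page shows an abnormal test procedure result. Protocol 10.5.2.2 reads only the completion page, so there is no event. Protocol 10.4.3 and SAP 2.8 censor at the date of discontinuation.
3. The same patient would appear in the SAP 2.8.1 table if that table is built from the AE action field. The SAP does not say so, but it is the natural source.
4. Change the completion-page reason to Adverse Event and the patient becomes an event. The loss therefore depends on the site's choice.

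**Illustration of size**

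The plan gives no event rate, effect size or power for this endpoint, so there is no figure to reproduce. From the documents: 210 patients randomized 2:1, which is 140 and 70. Assumed: true safety stops of 30% on deferasirox and 15% on placebo, and 20 to 40% of the drug-caused excess entered under an uncounted reason.

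- True stops: 0.30 × 140 = 42 and 0.15 × 70 = 10.5. Risk ratio 0.30 / 0.15 = 2.0.
- Background stops expected on deferasirox: 0.15 × 140 = 21. Drug-caused excess: 42 − 21 = 21.
- Events lost: 0.20 × 21 = 4.2 to 0.40 × 21 = 8.4.
- Remaining risk: (42 − 4.2) / 140 = 27% to (42 − 8.4) / 140 = 24%.
- Apparent risk ratio: 27 / 15 = 1.8 to 24 / 15 = 1.6.

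**Hazard-ratio scale**

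With constant hazards, HR = ln(1 − 0.30) / ln(1 − 0.15) = 2.19, and SE(log HR) = √(1/e_D + 1/e_P), where e_D and e_P are the counted events. If shares m_D and m_P of all stops are missed in the two arms, the HR is multiplied by (1 − m_D) / (1 − m_P).

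| Missed share, deferasirox / placebo | Events | HR (95% CI) |
|---|---|---|
| 0 / 0 | 42.0 / 10.5 | 2.19 (1.12–4.32) |
| 20% / 20% | 33.6 / 8.4 | 2.19 (1.03–4.67) |
| 20% / 0 | 33.6 / 10.5 | 1.76 (0.88–3.51) |
| 0 / 20% | 42.0 / 8.4 | 2.74 (1.31–5.75) |

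The third row, 8.4 of 42 events lost, is the upper end of the illustration above. An equal missed share leaves the ratio alone and widens the interval. A larger share missed on deferasirox pulls the ratio toward 1. A larger share missed on placebo pushes it away from 1.

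**The case against.** The strongest reply is that the protocol already steers safety stops toward the AE category. Section 6.7.5 sends them to the AE page. Section 7.5.1 treats clinically significant laboratory or test results, and those requiring interruption of study drug, as reportable AEs. Section 7.5.4 requires significant hearing and eye findings that meet the AE definition to be recorded as AEs. A site that follows this thinking will probably enter Adverse Event as the reason, and the stop then counts. The form's completion instructions are not in the documents, and nothing shows sites coding otherwise. This stands. A reader might infer that every stop for an abnormal hearing, eye or echocardiographic test is censored by rule; the text does not support that.

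The investigator-judgement wording says who decides, not which box to tick. The same part of the protocol also contains stops that are not worded as discretionary: the renal thresholds in 6.7.1.3, suspected Stevens-Johnson syndrome in 6.7.1.6.1, severe hepatic impairment in 6.7.1.7 and severe hypersensitivity in 6.7.1.9. So it would be wrong to say that toxicity stops in general are framed as the physician's choice.

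The direction of bias is not established. Reasons are entered in a double-blind trial, and no document shows coding that differs by arm.

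Finally, the AE table in SAP 2.8.1 gives partial cover, and using the recorded reason is a defensible definition that matches the endpoint's name. What the objection does not answer is that the table does not feed the time-to-event variable, so a patient flagged on the AE page as stopping because of an AE can still be censored here.

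**Conclusion.** The definition is narrower than the data collected allow, and it can miss safety stops and disagree with the AE table. That follows from the text. How often it would happen does not: it depends on how sites choose among the 14 reasons.

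Under the stated assumptions (30% against 15%, with 20 to 40% of an excess of 21 events coded elsewhere), about 4 to 8 deferasirox events are lost and the risk ratio falls from 2.0 to about 1.8–1.6. A reader might apply the 20 to 40% to all 42 deferasirox stops and reach 24 / 15 = 1.6 down to 18 / 15 = 1.2. That would require background stops to be miscoded on deferasirox but not on placebo, and nothing in the documents supports it. Nor do they support saying that the hazard ratio is biased toward 1. It could be, if more stops are missed on deferasirox.

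This is one of five secondary safety endpoints, with an exploratory test and unadjusted intervals. It should not be called the trial's tolerability endpoint, since Protocol 10.5.4 marks tolerability as not applicable. The point is worth correcting because the correction is cheap, not because it threatens the main conclusions.

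**What to change.** In Protocol 10.5.2.2 and SAP 2.8, before unblinding:

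- Define the event as a completion-page reason of Adverse Event, Abnormal laboratory value(s) or Abnormal test procedure result(s), **or** any AE record whose action taken is permanent discontinuation of study drug. Date it at study drug discontinuation, as now.
- Do not count stops driven by a primary endpoint event confirmed by the Endpoint Adjudication Committee (cardiac, liver or AML). Censor them at discontinuation and show them separately. This carve-out is needed because Protocol section 4 ends treatment on a confirmed non-fatal endpoint event, and 7.5.7 and 7.5.10 send heart failure and liver events to the AE page. The wider definition would otherwise draw efficacy events into a toxicity endpoint.
- Keep the two-reason definition as a sensitivity analysis.
- Use one name for the form: 10.5.2.2 calls it the Study Treatment Completion page and 6.7.6.1 the End of Treatment page.

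Both fields are already collected, so the cost is revised wording and a little extra programming, mainly for the carve-out. The reported discontinuation rate would probably be slightly higher.

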#### 10.5.2.3 Adverse events (AE)

Frequency tables for treatment-emergent AEs (see Section 10.5.2.1) will present, for each treatment group, the number of patients and the percentage of patients experiencing the AE. Multiple occurrences of the same event in the same patient will be counted only once in the frequency tables. However, all adverse events will be included in the AE listings.

Frequency tables will display at least the MedDRA system organ class and preferred term, AE severity (mild, moderate, severe), and relationship to study drug.

Deaths reportable as SAEs and non-fatal serious adverse events will be listed by patient and tabulated by MedDRA preferred term and treatment group.

## 10.5.2.4 Analysis of laboratory data

For analyzing laboratory data, data from all sources (central and local laboratories) will be combined. Other than for weekly serum creatinine monitoring visits, central laboratory results are the only laboratory results that will be captured in the database.

#### **Grading of laboratory data**

For laboratory tests covered by the Common Terminology Criteria for Adverse Events (CTCAE) version 3.0 NCI 2006, the study's biometrics team will grade laboratory data accordingly with the exception of grade 5 (death). For laboratory tests covered by CTCAE, a grade 0 will be assigned for all non-missing values not graded as 1 or higher. For laboratory tests where grades are not defined by CTCAE, results will be graded by the low/normal/high classification based on laboratory normal ranges.

#### Reporting of laboratory data

The following by-treatment summaries will be generated separately for hematology, biochemistry and urinary laboratory tests:

- Frequency table for newly occurring on-treatment grades 3 or 4.
- Shift tables using CTCAE grades to compare baseline to the worst on-treatment value.
- For laboratory tests where CTCAE grades are not defined, shift tables using the low/normal/high/(low and high) classification to compare baseline to the worst ontreatment value.

For a specific laboratory test, patients with newly occurring on-treatment grade 3 or 4 are defined as:

- Patients with baseline grade missing, 0, 1 or 2 and worst on-treatment grade 3 or 4 (percentage to be based on all patients with baseline grade missing, 0, 1 or 2).
- Patients with baseline grade missing, 0, 1, 2 or 3 and worst on-treatment grade 4 (percentage to be based on all patients with baseline grade missing, 0, 1, 2 or 3).

The following listings will be generated:

- Listing of laboratory data for patients with newly occurring grade 3 or 4 laboratory toxicities.
- Listing of laboratory data for patients with values outside the laboratory normal ranges with values flagged to show the corresponding CTCAE grades and the classifications relative to the laboratory normal ranges.
- Listing of all laboratory data with values flagged to show the corresponding CTCAE grades and the classifications relative to the laboratory normal ranges.

#### 10.5.3 Other safety data

Data from other safety tests or assessments will be summarized descriptively and listed, with notable values flagged.

#### 10.5.4 **Tolerability**

Not applicable.

#### 10.5.5 **Pharmacokinetics**

Not applicable.

#### 10.5.6 **Biomarkers**

Not applicable.

#### 10.6 Interim analysis

No interim analysis will be performed.

#### 10.7 Sample size calculation

The foreseen sample size of 210 patients randomized in a ratio of 2:1 in favor of deferasirox is based on the feasibility of enrolling the patients and consultations with the Health Authorities.

#### 10.8 Power for analysis of critical secondary variables

Power calculations for secondary variables were not done for the determination of sample size.

#### 11 Administrative procedures

#### Regulatory and ethical compliance

This clinical study was designed and shall be implemented and reported in accordance with the protocol, the International Conference on Harmonization (ICH) Harmonized Tripartite Guidelines for GCP, with applicable local regulations (including European Directive 2001/20/EC and US Code of Federal Regulations Title 21), and with the ethical principles laid down in the Declaration of Helsinki.

## Responsibilities of the investigator and IRB/IEC/REB

The protocol and the proposed informed consent form must be reviewed and approved by a properly constituted Institutional Review Board/Independent Ethics Committee/Research Ethics Board (IRB/IEC/REB) before study start. A signed and dated statement that the protocol and informed consent have been approved by the IRB/IEC/REB must be given to Novartis before study initiation. Prior to study start, the investigator is required to sign a protocol signature page confirming his/her agreement to conduct the study in accordance with these documents and all of the instructions and procedures found in this protocol and to give access to all relevant data and records to Novartis monitors, auditors, Novartis Clinical Ouality Assurance representatives, designated agents of Novartis, IRBs/IECs/REBs and regulatory authorities as required.

